3.4.3 SBRT

Modifications of RT doses during SBRT due to local or systemic toxicities will be made at the discretion of the treating radiation oncologist. Early side effects happening during or shortly on or after treatment like fatigue, nausea, vomiting, abdominal cramps, diarrhea and skin changes tend to be short-term and treatable and will be managed with standard supportive care measures. In the rare event of pre-treatment leukopenia or thrombocytopenia, the following guide for dose adjustments of SBRT should be followed first:

Table 15: Recommended Dose Reductions for Myelosuppression

Absolute granulocyte count, $\times 10^6/L$		Platelet count, $\times 10^6/L$	% of selected starting dose
$\geq 1,000$	And	$\geq 85,000$	OK to treat
$< 1,000$	Or	$< 85,000$	Do not start RT

Hold SBRT for hematological toxicity until resolved to grade ≤ 1 . If not resolved within 2 weeks, discontinue SBRT.

Dose Modifications for Non-Hematologic Adverse Reactions requiring permanent discontinuation of SBRT for any of the following:

- Severe grade 3 or higher hepatic toxicity
- \geq grade 3 GI bleeding or GI perforation

Hold SBRT (Grade 3 or 4) for other non-hematological toxicity until resolved to grade ≤ 1 . If not resolved within 2 weeks, discontinue SBRT.

No dose modifications are recommended for alopecia, nausea, or vomiting.

3.4.3.1 Management of radiation-treatment related pain (radiation-induced pain flare)

The prophylactic use of dexamethasone or any other steroids is not allowed. Patient should be proactively managed with signs of radiation-induced pain flare which includes early hospital admission with adequate use of oral and intravenous combination analgesics as required. A pain scale should be established early and frequently repeated, patients should be assessed after baseline persistent pain has been stabilized with around-the-clock (ATC) analgesics on regular intervals. Short-acting opioid analgesics are the primary treatment, dose and/or dosing frequency of the ATC analgesic should be adjusted for patients with end-of-dose radiation-induced pain flare. Short-acting oral opioids can be considered when given preemptively in patients with predictable radiation-induced pain flare.

Hospital admission exceeding 1 week for management of radiation-induced pain flare should be considered grade 3 AE, hospital admissions to accommodate pain management for radiation-induced pain flare ≤ 7 days grade 2 AE.

3.5 ASSESSMENTS ON TREATMENT

3.5.1 Study assessments

Study assessments are presented in Study Calendar [3.8](#).

3.5.2 End-of-Treatment Visit and Follow UP

See Study Calendar, Section [3.8](#).

3.5.3 Treatment pauses for surgery

Surgery is not part of this protocol and will be done as standard of care procedure with enrollment of patient to another surgical protocol at the NIH Clinical Center or at home institution.

If during the treatment patient's tumors become resectable per standard of care, M7824 and/or M9241 will be stopped at least 5 days prior to the scheduled date of surgery.

If surgery performed outside NIH, we will ask patients to provide the outside surgical pathology report for determination of resection status (R0, R1, R2) and tumor sample from this surgery for research.

If surgical exploration does not result in a successful removal of the tumor as defined below:

- R0: closest tumor ≥ 1 mm from surgical resection margin
- R1: tumor within < 1 mm of surgical resection margin

- R2: involvement of surgical resection margin with tumor (incomplete tumor clearance)
- “open and close”

treatment with M7824 and M9241 will resume 6-8 weeks after surgery when patient recovers. SBRT will not be repeated.

If surgical exploration results in a successful removal of the tumor, patient will be taken off study treatment.

Before post-surgery re-treatment with M7824 and M9241, Day 1 the following tests and examinations must be performed to evaluate safety of re-treatment and estimate baseline for tumor evaluations:

Within 28 days:

- CT/MRI of chest, abdomen and pelvis;
- Research Quality of Life assessment (subject-reported outcomes / symptom severity assessments the 4th version of the ‘Functional Assessment of Cancer Therapy with the hepatobiliary and pancreatic specific module ([Appendix C](#)). (For English speaking subjects only)

Within 3 days:

- Physical examination, including weight, vital signs, EKG, and ECOG performance status;
- Adverse event and concomitant medications;
- Laboratory evaluation:
 - Hematological profile: CBC with differential and platelet count;
 - Biochemical profile: Acute care panel (that includes sodium, potassium, BUN, creatinine), Hepatic panel (that includes AST, ALT, total bilirubin), Mineral panel (that includes calcium, phosphorus, albumin, and magnesium), and uric acid;
 - CEA, CA19-9, CA-125
 - T4, TSH
 - Amylase/ lipase
 - Serum or urine pregnancy test for female participants of childbearing age (in the absence of prior hysterectomy)
 - Urinalysis.

Research blood will not be collected during post-surgery treatment

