At Cycle 3 Day 15 (+/- 7 days) patient will undergo imaging and every 2 Cycles (+/-5 days) thereafter.

[figure not shown]
If during the treatment patient's tumors become resectable per standard of care, M7824 and/or M9241 will be stopped at least 5 days prior to the scheduled date of surgery. Surgery is not part of this protocol and will be done as standard of care procedure with enrollment of patient to another surgical protocol in NIH or at home institution.

If surgical exploration does not result in a successful removal of the tumor, patient will be able to return to treatment following recovery from surgery (See section 3.5.3). If tumor removed successfully, patient will be taken off protocol treatment.

Schema 1: Phase IA.

Schema 2: Phase IB

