3.11.1 Criteria for Removal from Protocol Therapy

- Patient request to be withdrawn from therapy
- Progressive disease as defined in section 6.3. Subjects should continue treatment beyond the initial determination of PD, through their next tumor assessment, which in this case should be in 4 weeks if:
 - There are no new Grade 2 or greater symptoms or significant worsening of existing symptoms.
 - There is no increase in ECOG.
 - There are no new metastatic lesions
 - In the opinion of the Investigator, the subject does not require new anticancer therapy.
- Excessive toxicity (see section 3.4)
- Necessity to administer a non-permitted concomitant drug (see section 4.2)
- Surgical exploration results in a successful removal of the tumor
- PI discretion
- Positive pregnancy test
- The drug manufacturer can no longer provide the study agents

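### Section 3.5.3 lists R0 among the unsuccessful surgical outcomes that restart M7824 and M9241, leaving no listed outcome for the rule that successful removal ends protocol treatment

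*Combined protocol and SAP*

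**What the plan says.** Section 3.5.3 of the combined protocol and SAP governs what happens to study treatment after surgery. Its restart rule begins "If surgical exploration does not result in a successful removal of the tumor as defined below" and is followed by four bullets:

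- "R0: closest tumor ≥ 1 mm from surgical resection margin"
- "R1: tumor within < 1 mm of surgical resection margin"
- R2, margin involved by tumor, glossed as incomplete clearance
- open-and-close

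The sentence then finishes: "treatment with M7824 and M9241 will resume 6-8 weeks after surgery when patient recovers". SBRT is not repeated.

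The next rule in the same section points the other way: "If surgical exploration results in a successful removal of the tumor, patient will be taken off study treatment". Section 3.1 repeats it: "If tumor removed successfully, patient will be taken off protocol treatment". Section 3.11.1 makes it a formal criterion for stopping protocol therapy: "Surgical exploration results in a successful removal of the tumor". Section 3.1 sends the reader to 3.5.3 for the conditions of returning to treatment. No other section defines successful removal.

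**The concern.** The restart rule and the off-treatment rule are meant to divide surgical outcomes between them. As drafted, the restart list contains every resection category plus open-and-close, so the off-treatment rule has nothing to act on. The item that plainly does not fit is R0.

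This is an operative dosing instruction, not background text. It decides whether a patient whose tumor has been cleared receives further M7824 and M9241. What is at stake is unneeded post-operative exposure to two investigational agents. There is also a gap for R1: once the list is known to contain an error, its placement of R1 cannot be taken as settled.

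**Working it through.** The plan states no figure on this point, so the check sets the provisions side by side and counts outcomes.

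**Step 1. Read the list as defining unsuccessful removal**, which is its grammatical sense.

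| Outcome | Restart rule (3.5.3) | Left for off-treatment rule (3.5.3, 3.1, 3.11.1) |
|---|---|---|
| R0 | resumes | no |
| R1 | resumes | no |
| R2 | resumes | no |
| Open-and-close | resumes | no |
| Total | 4 of 4 | 0 of 4 |

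**Step 2. Try the other readings.**

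- If the list defined successful removal, R2 and open-and-close would be successes. R2 is described in the list itself as incomplete clearance, so this fails.
- If the list were only a glossary of resection status, the protocol would nowhere say which categories restart and which stop. Open-and-close is also an outcome, not a margin definition, and the sentence still ends in resumption.

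No reading yields a usable rule without a correction.

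**Step 3. Identify the misplaced item.** Section 1.2.1 equates R0 with margin-negative resection, associates it with the best outcomes, and names conversion to an R0 resection as part of the main goal of neoadjuvant therapy. Section 3.5.3 also asks for scans before restart to set a new tumor baseline, which fits residual disease better than a cleared margin. R0 is therefore the item that does not belong.

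**Step 4. Count after correcting R0.** R0 goes off treatment (1 of 4). R2 and open-and-close resume (2 of 4). R1 is undecided (1 of 4). Depending on the sponsor's answer, 2 + 1 = 3 of 4 resume, or 2 of 4 do.

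**Step 5. Exposure for a patient restarted in error.** Section 3.1 gives M7824 on Days 1 and 15 and M9241 on Day 1 of each 28-day cycle. At 1,200 mg per infusion (Tables 5 and 6), that is 2 × 1,200 mg = 2,400 mg of M7824 and one M9241 injection per cycle. This is the ordinary schedule applied to one hypothetical patient, not an estimate of trial-wide effect.

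**The case against.** The strongest defense is that the meaning is obvious. Just before the restart rule, 3.5.3 asks for outside pathology reports so that resection status can be classed as R0, R1 or R2. Three of the four bullets read as definitions. A glossary was probably run into a rule. Several provisions then point the right way: the off-treatment rule appears in 3.5.3, 3.1 and 3.11.1, and the précis allows restart only where removal failed. The précis and 3.1 word restart as something a patient may do, and 3.11.1 lets the investigator or the patient end therapy. All of this stands and makes re-dosing of an R0 patient unlikely. It does not remove the conflict, because 3.5.3 is where 3.1 sends the reader and its wording there is mandatory.

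Three stronger readings are tempting, and the documents do not support them.

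- A reader might infer a distinct surgical hazard, since Tables 11 and 12 name bleeding and impaired wound healing as M7824 risks. But Table 12 recommends a hold of roughly 4 weeks after major surgery, and the 6-8 week restart, conditional on recovery, is later than that. The same risks apply to R1, R2 and open-and-close patients. What is specific to R0 is unneeded exposure.
- A reader might infer that R1 clearly resumes, so that 3 of 4 outcomes restart after correction. R1 is literally in the list, and 1.2.1 reports poor outcomes without a margin-negative resection. That is prognosis, not a dosing rule, and only R2 is labeled incomplete clearance. Either placement of R1 is open.
- A reader might infer that the efficacy results are compromised. The endpoint definitions in 10.1.2 and the analyses in 10.4 do not depend on this list. Time-to-recurrence still runs from resection to recurrence.

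**Conclusion.** The inconsistency is real and is in the current text. By the letter of 3.5.3, 4 of 4 listed surgical outcomes restart treatment and 0 of 4 remain for the rule that ends it. That R0 counts as success is an inference from its definition and from 1.2.1, because successful removal is never defined, but the inference is a safe one.

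The practical consequence is limited to possible unneeded post-operative treatment of completely resected patients, and the surrounding text makes that improbable. No number of affected patients can be given: the documents state no expected R0 share for this population and regimen. The primary and secondary endpoints, the sample size and the Simon two-stage rule are unaffected. The text should still be corrected, because a dosing rule should be executable as written and the correction costs almost nothing.

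**What to change.** In 3.5.3:

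1. Remove the R0 bullet from the restart list.
2. State that R0 is a successful removal and ends protocol treatment.
3. Keep R2 and open-and-close as outcomes after which M7824 and M9241 resume.
4. Add one sentence, decided by the sponsor, saying whether R1 resumes (its present literal placement) or comes off treatment.

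In 3.1 and 3.11.1, cross-refer to this definition.

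The cost is wording only: one bullet moved, one definition, one sponsor decision on R1 and two cross-references. Resection status is already collected (3.5.3 and 6.1.3), so data collection does not change. Sections 10.1.2 and 10.4.3 need no edit.

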3.6 QUESTIONNAIRES

The rationale for questionnaires is discussed in Section [1.2.8](#) and timing is specified in Study Calendar [3.8](#). The average time to complete these instruments is 20 minutes. For English speaking subjects only.

3.7 RESEARCH IMAGING

K_{trans} and K_{ep} perfusion measure of tumoral lesions measured on DCE-MRI with contrast will be measured at baseline, before treatment on day 1 of cycles 1 (+/-5 days) and 3 (+/-5 days). The scheme ensures perfusion measurements

- At baseline in the absence of M7824 and M9241
- After M7824 administration only (examining the effect of M7824 as a stromal modulator only; the anti-TGF β component of the dual checkpoint inhibitor M7824 has been shown to act as a stromal modulator increasing perfusion in preclinical models as well as in few patients enrolled on 18-C-0061; M7824 in combination with gemcitabine in advanced pancreas cancer)
- After combined M7824 and M9241 (two doses) administration; this timepoint examines if the addition of M9241 alters the stroma and perfusion.

Patients in Cohort 1A only.

3.8 STUDY CALENDAR

Procedure	Screening	Baseline ¹	Day -14 ¹	Cycles (28+/- 3 days) ¹		EOT visit ^{13, 16}	28 Days FU ^{14, 16}	Long Term FU ^{15, 16}
				Day 1	Day 15			
M7824 ²			X	X	X			
M9241 ³				X				
SBRT ⁴					X (C1 only)			
Medical History	X							
Confirmation of Pathology	X							
Height	X							
Physical exam, weight, vital signs, ECOG ^{5, 17}	X	X		X	X	X	X	
Skin assessment		X		X ¹⁸			X	
EKG ¹⁷	X	X		X ⁶	X ⁶		X	
CBC with differential and platelets ¹⁷	X	X	X	X	X	X	X	
Biochemical profile ^{7, 17}	X	X	X	X	X	X	X	

Abbreviated Title: M7824, M9241 and SBRT

Version date: 11/10/2021

Procedure	Screening	Baseline ¹	Day -14 ¹	Cycles (28+/- 3 days) ¹		EOT visit ^{13, 16}	28 Days FU ^{14, 16}	Long Term FU ^{15, 16}
				Day 1	Day 15			
Pregnancy testing (urine or serum) ¹⁷	X	X		X				
A brain CT / MRI scan if clinically indicated	X							
Tumor evaluation ^{8, 17}	X	X		X (odd cycles, except C3)	X (C3 only)			X
CEA, CA19-9, CA-125 ¹⁷		X		X		X	X	
T4 and TSH ¹⁷		X		X		X	X	
Amylase / lipase ¹⁷		X		X		X	X	
Urinalysis ¹⁷		X		X		X	X	
PT, INR, aPTT, fibrinogen		X		X			X	
Concomitant Medications ¹⁷		X		X		X	X	
Baseline symptom collection		X						

Abbreviated Title: M7824, M9241 and SBRT

Version date: 11/10/2021

Procedure	Screening	Baseline ¹	Day -14 ¹	Cycles (28+/- 3 days) ¹		EOT visit ^{13, 16}	28 Days FU ^{14, 16}	Long Term FU ^{15, 16}
				Day 1	Day 15			
Collection of archival tumor sample if available for research		X						
FACT-Hep ^{9, 17}		X		X				
Adverse events ¹⁷			X	X	X	X	X	X
Research MRI ¹⁰		X		X				
Research blood for PK ¹¹			X	X	X			
Research blood for ADA sampling		X		X ¹²				
Research blood for Cytokines and TNF		X		X				
Research blood for circulating free tumor DNA (cfDNA) assay		X		X		X		
Phone call or e-mail								X

¹ Baseline and Day -14 (Arm 1A) or C1D1 (Arm 2A and Arm 3) evaluations do not need to be repeated if performed at screening or baseline in designated time frame. All evaluations will be done within 72 hours before treatment initiation on treatment days. If treatment does not start within 28 days after enrollment, screening evaluations will be repeated.

² M7824 will be administered as an IV on Days 1 and 15 of every cycle. **Note:** Additional infusion on Day -14 in Arm 1A.

³ M9241 will be administered as a subcutaneous injection on Day 1 of every cycle.

⁴ SBRT Radiation therapy on Day 17 (+5 days) of Cycle 1 and continue for 5 consecutive business days (except federal holidays). It will be administered as short course (SBRT) of 5 fractions according to schedule assigned by radiation oncologist.

⁵ Eye signs and symptoms and assessment of skin should be included into physical exam. If clinically indicated, ophthalmology and dermatology consults should be ordered.

⁶ Cycle 1 only, before study treatment.

⁷ Biochemical profile: Acute care panel (that includes sodium, potassium, BUN, creatinine), Hepatic panel (that includes AST, ALT, total bilirubin), Mineral panel (that includes calcium, phosphorus, albumin, magnesium), uric acid

⁸ CT of chest, abdomen and pelvis (or MRI of chest, abdomen and pelvis if clinically indicated). Cycle 3 day 15 (+/- 5 days) and every 2 Cycles (+/-5 days) thereafter. If patient is taken off treatment for reason other than disease progression, imaging evaluations will continue during follow up period every 12 weeks (\pm 2 weeks) until progression. In addition, if PD, a confirmatory scan should be obtained 4 weeks (+ 1 week) following initial documentation of PD.

⁹ Research Quality of Life assessment (subject-reported outcomes / symptom severity assessments the 4th version of the 'Functional Assessment of Cancer Therapy with the hepatobiliary and pancreatic specific module (**Appendix C**)). (For English speaking subjects only. At baseline, cycles 2, 4 and every 12 weeks after that.

¹⁰ At baseline, before treatment on day 1 of cycles 1 and 3 (+/-5 days). Cohort 1A only.

¹¹ See Section **5.1.3**

¹² Before dosing on Cycle 2 day 1

¹³ All subjects should undergo an End-of-Treatment visit after discontinuation of M7824 and M9241 for any reason. This visit should be performed on the day of or within 7 days after the decision to discontinue trial treatment but before any new antineoplastic therapy is started (if possible), whichever occurs earlier. Research samples may be collected as logistically feasible. If it is known to the Investigator at the time of the End of-Treatment visit that the subject will start new treatment within 28 days of last treatment or they will be unable to return within 28 days of last treatment, assessments associated with the 28-Day Safety Follow-up visit may be conducted at the End-of-Treatment visit.

Abbreviated Title: M7824, M9241 and SBRT

Version date: 11/10/2021

¹⁴ A Safety Follow-up visit is scheduled 4 weeks (28 ± 5 days) after the last administration of M7824 or M9241 but before any new therapy is started, if possible, whichever occurs earlier. All SAEs ongoing at the 28-Day Safety Follow-up visit must be monitored and followed up by the Investigator until stabilization or until the outcome is known, unless the subject is documented as “lost to follow-up.” In addition, all trial drug-related SAEs occurring after 28 Day Safety Follow up visit and ongoing at the Safety Follow-up visit have to be followed up in the same manner

¹⁵ Subjects with PD will be followed every 12 weeks (± 2 weeks) by phone or e-mail for survival and further tumor therapy for 1 year after the last dose of study drug. After 1-year subjects will be followed for survival every 6 month. Subjects without progressive disease at 28-Day Safety Follow-up visit will be invited to Clinical Center to perform CT scans (or MRI scans if clinically indicated) every 12 weeks (± 2 weeks) until PD. Outside scans are acceptable.

¹⁶ If subjects are not willing to come to NIH after treatment discontinuation for FU visits, they will be followed by phone call or e-mail.

¹⁷ Must be done before re-treatment after surgery.

¹⁸ Every 6 weeks

3.9 COST AND COMPENSATION

3.9.1 Costs

NIH does not bill health insurance companies or participants for any research or related clinical care that participants receive at the NIH Clinical Center. If some tests and procedures performed outside the NIH Clinical Center, participants may have to pay for these costs if they are not covered by insurance company. Medicines that are not part of the study treatment will not be provided or paid for by the NIH Clinical Center.

3.9.2 Compensation

None.

3.10 REIMBURSEMENT

The NCI will cover the costs of some expenses associated with protocol participation. Some of these costs may be paid directly by the NIH and some may be reimbursed to the participant/guardian as appropriate. The amount and form of these payments are determined by the NCI Travel and Lodging Reimbursement Policy.

3.11 CRITERIA FOR REMOVAL FROM PROTOCOL THERAPY AND OFF STUDY CRITERIA

Prior to removal from study, efforts must be made to have all subjects complete a safety visit approximately 28 days following the last dose of study therapy.

3.11.1 Criteria for Removal from Protocol Therapy

- Patient request to be withdrawn from therapy
- Progressive disease as defined in section 6.3. Subjects should continue treatment beyond the initial determination of PD, through their next tumor assessment, which in this case should be in 4 weeks if:
 - There are no new Grade 2 or greater symptoms or significant worsening of existing symptoms.
 - There is no increase in ECOG.
 - There are no new metastatic lesions
 - In the opinion of the Investigator, the subject does not require new anticancer therapy.
- Excessive toxicity (see section 3.4)
- Necessity to administer a non-permitted concomitant drug (see section 4.2)
- Surgical exploration results in a successful removal of the tumor
- PI discretion
- Positive pregnancy test
- The drug manufacturer can no longer provide the study agents

3.11.2 Off -Study Criteria

- Death

- Patient request to be withdrawn from study
- Lost to follow up
- PI discretion
- PI decision to end the study

3.11.3 Lost to Follow-up

A participant will be considered lost to follow-up if he or she fails to return for 3 scheduled visits and is unable to be contacted by the study site staff.

The following actions must be taken if a participant fails to return to the clinic for a required study visit:

- The site will attempt to contact the participant and reschedule the missed visits and counsel the participant on the importance of maintaining the assigned visit schedule and ascertain if the participant wishes to and/or should continue in the study.
- Before a participant is deemed lost to follow-up, the investigator or designee will make every effort to regain contact with the participant (where possible, 3 telephone calls and, if necessary, a certified letter to the participant's last known mailing address or local equivalent methods). These contact attempts should be documented in the participant's medical record or study file.
- Should the participant continue to be unreachable, he or she will be considered to have withdrawn from the study with a primary reason of lost to follow-up.

